Resuscitation scenario: the untimed portion of the simulation starts by turning on the video cameras and the fitness watch. The paramedic and both investigators (the confederate paramedic and the physician) wait outside the room where they are supposedly dispatched. The team will be invited to enter the room by the father (simulated by the technician operating the manikin). A clinical statement to recognize the life-threatening condition of the patient, including his weight and age, is then given by the father as follows: "Here is Junior, a 12-kg, 1 and a half year old boy who suddenly collapsed 15 minutes ago. Oral tricyclic antidepressant as well as antidiabetic pills from his grandmother were found in his mouth and on the ground of his room. He is unconscious, pale and does not breathe". At this moment, the physician asks the participant to take a central pulse. Because of the invariable absence of a pulse, the latter is asked to assist the physician to perform a 2-min full course massage and ventilation (15:2 ratio) maneuver to increase his own stress level (massage carried out by the participant). During this time, the physician asks the confederate paramedic to place a 4-derivation electrocardiogram on the manikin, an upper arm blood pressure monitor, a digital pulse oximeter and defibrillator's patches. Then the physician asks to change roles; the confederate paramedic has to carry out the massage while the participant has to get a peripheral vascular access on the manikin's right hand. At this time, an asystole rhythm is recognized and verbalized by the physician. On the basis of the American Heart Association pediatric cardiac arrest algorithm for asystole⁴, a bolus of epinephrine is ordered by the physician and the timed scenario begins. The participant must prepare and administer the drug with the help of PedAMINES (intervention group) or following the conventional method. ROSC ensues with generalized tonic-clonic seizures. The physician says: "The patient has now a return of spontaneous circulation with a pulse but with seizures. This patient needs an IV bolus of midazolam right now". The seizures stop 15 seconds after administration of the drug. At this time the physician asks the participant to perform a finger stick to obtain a blood sample. The glucometer reports a blood sugar of 0.8 mmol/L. The physician says: "the patient has a severe

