hypoglycemia” and prompts the participant to prepare and inject an IV bolus of dextrose 10%. Return of a state of consciousness ensues with normal vital signs, but a wide QRS on EKG-monitoring. The physician says: “This child needs an IV bolus of sodium bicarbonate 1 mEq/kg”. As soon as this last medication is administered, the physician asks for transport and the scenario ends. The cameras and the watch are turned off 1 minute later. The measured deviation between the amount of drug delivered and the actual prescribed dose will be measured by the amount of drug in the syringe. As everything is video-recorded, we will be able to verify and measure the exact amount of drug and concentration in the syringe after the scenario. During the whole scenario, the physician, the confederate paramedic and the operator will maintain a stressful resuscitation atmosphere (monitoring alarms are on, the primary assessment (ABCDE) is often repeated, vital signs are frequently reported aloud and the father repeatedly verbalizes his dismay).

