C) *Questionnaires*: at the end of the scenario, a 6-item questionnaire using a 10-point Likert scale (scored from one to ten to avoid neutral answers) will be provided to the participants. The questionnaire measures (1) the overall stress perceived, (2) the stress perceived during each drug preparation sequence with PedAMINES and with the conventional method(s), and (3) the satisfaction about the preparation method used during the resuscitation scenario. Acceptability and usability testing of the app will be assessed using a 52-item questionnaire based on the unified theory of acceptance and use of technology (UTAUT) model⁵⁴. UTAUT provides a useful tool to assess the likelihood of success for new technology introductions and helps to understand the drivers of its acceptance.

D) *Heart rate (HR) as a stress marker*: a baseline HR before the beginning of the scenario as well as continuous HR monitoring of each participant reflecting his or her stress level will be recorded during the scenario. Mean delta HR values (difference between HR peak values and baseline HR) will be obtained during some small segments of scenario and correlated to the scenario phases and the preparation methods used.

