2.3.7. Patients Timeline

On-site staff in every collaborating EMS will organize participation of paramedics to the study. No information about the ongoing study will be given to the paramedics at this stage. The best study period will be matched with study coordinators. The paramedics will be spread throughout 1 week in order to link up the several scenarios. On scheduled weeks, the study coordinators will visit the collaborating EMS, provide trial information to participants before they begin the scenario, and assessment of eligibility will be verified. Participants will then sign the informed consent. They will be asked to complete an anonymised demographic questionnaire and confirm their willingness to participate. If it's the case, they will pursue with a 5-minute learning session to the use of PedAMINES given by the investigators. Then, each participant will be randomly allocated to study arms. Immediately after the randomization, the paramedic will start the scenario. 1) the overall stress perceived during the scenario and during each drug preparation, and 2) the satisfaction about the preparation method used. The total study period to enroll all paramedics in the various EMS will take 12 months.

Table 1. PedAMINES timeline protocol for forms and procedures

	Study Period				
	Pre-enrollment	Enrollment / consent	Pre-study baseline / allocation	20-minute scenario	Closeout
Time point	$-t_2$	$-t_1$	0	t_1	t_x
ENROLMENT:					
Invitation to participate	X				
Eligibility screen		X			
Informed consent form		X			
Demographic questionnaire			X		
PedAMINES learning session			X		
Randomization			X		
INTERVENTION :					
Group A (with PedAMINES)				X	
Group B (with conventional method)				X	
Termination questionnaire					X
ASSESSMENTS :					
Medication errors				X	
Time at prescription				X	
Time to drug preparation (TDP) and delivery (TDD)				X	

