2.3.10.2. Concealment mechanism

Allocation concealment will be ensured with <http://www.sealedenvelope.com> and will not be released until the paramedics start the scenario.

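### The only heart-rate recording described that could serve as baseline starts after randomisation, so delta HR may subtract an arm effect

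*Combined protocol and SAP*

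**What the plan says.** Section 2.3.6 D asks for "a baseline HR before the beginning of the scenario as well as continuous HR monitoring of each participant". It then defines the outcome: "Mean delta HR values (difference between HR peak values and baseline HR) will be obtained during some small segments of scenario", to be "correlated to the scenario phases and the preparation methods used".

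Section 2.3.5.1, under the resuscitation scenario, gives the only switch-on of the watch: "the untimed portion of the simulation starts by turning on the video cameras and the fitness watch". The participant and the two study team members then "wait outside the room where they are supposedly dispatched", for a time that is not stated, until the father calls them in. At the end, "The cameras and the watch are turned off 1 minute later". Section 2.3.12.1 describes heart-rate recording over the whole scenario. Table 1 has no heart-rate row.

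On allocation, the sections differ:
- 2.3.5.1 puts randomisation before the 5-minute app training.
- 2.3.7 puts it after the training: "Immediately after the randomization, the paramedic will start the scenario".
- 2.3.10.2 says that the allocation "will not be released until the paramedics start the scenario".
- 2.3.11.1 says that paramedics are unblinded once randomised.

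For the analysis of heart rate, 2.3.14.2 plans Pearson correlations between the watch measures and the scenario phases, by drug and preparation method.

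**The concern.** A change score compares arms fairly if its baseline is untouched by allocation. Here nothing described secures that. The watch goes on after randomisation, and a participant who knows at the door whether the app will be available may be more or less tense for that reason. That reaction belongs to the stress under study, yet delta HR would subtract it.

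Adjusting for the same baseline as a covariate would not reliably repair this, since the covariate may itself be affected by allocation. Nor could an earlier reading be recovered later if the watch was not running. At stake is the interpretation of measured stress, which the summary in section 1 lists among the secondary outcomes.

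**Working it through.** **Order of events.** The documents give no heart-rate figure to reproduce, so the first check is the sequence.

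| Step | 2.3.5.1 | 2.3.7 |
|---|---|---|
| 1 | Demographic questionnaire | Demographic questionnaire |
| 2 | Randomisation | App training |
| 3 | App training | Randomisation |
| 4 | Watch on, wait outside the room | Scenario starts at once |
| 5 | Entry, resuscitation, drug orders | – |

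Two facts hold under either order. Randomisation precedes the watch, and the questionnaire precedes randomisation.

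**Which recorded segment could be the baseline?** After entry, the untimed portion includes 2 minutes of chest compressions by the participant, meant to raise his or her stress, so it cannot serve as a baseline. That leaves the wait outside the room.

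**Is the arm known by then?** Sections 2.3.5.1 and 2.3.11.1 allow it. Section 2.3.10.2 ties release to the scenario start, which is about when the watch goes on, and does not settle which comes first.

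**What the subtraction does.** Write P for mean peak HR and B for mean baseline HR, in arms A (app) and C (control):

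difference in delta HR = (P_A − P_C) − (B_A − B_C)

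With a pre-allocation baseline, the expected value of B_A − B_C is 0 by randomisation. With a post-allocation baseline it need not be 0, and whatever it is enters with its sign reversed.

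**Illustration 1 (all bpm values assumed).** Suppose that peak HR is 8 bpm lower with the app, so P_A − P_C = −8.
- App baseline lower by 2, 4 or 6: −8 + 2 = −6, −8 + 4 = −4, −8 + 6 = −2. The contrast shrinks by 25%, 50% or 75%.
- App baseline higher by 2, 4 or 6: −10, −12, −14. The contrast is inflated by the same amounts.

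**Illustration 2 (SD and shift assumed).** Take 60 per arm (2.3.8), a two-sided 5% test, no difference in peak HR and a baseline shift of b bpm. With Φ the standard normal distribution function:

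SE = SD × √(2/60); P(significant) = Φ(b/SE − 1.96) + Φ(−b/SE − 1.96)

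For SD 15, SE = 15 × 0.1826 = 2.74. At b = 5, b/SE = 1.83 and the probability is 45%.

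| Assumed SD | b = 0 | b = 2 | b = 5 | b = 8 |
|---|---|---|---|---|
| 10 bpm | 5% | 20% | 78% | 99% |
| 15 bpm | 5% | 11% | 45% | 83% |
| 20 bpm | 5% | 9% | 28% | 59% |

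The protocol plans no such test; the table only shows how sensitive one would be.

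**Sample size.** It takes no heart-rate input. For 60% versus 30%, 90% power and two-sided 5%, the pooled-variance formula gives [1.960 × √(2 × 0.45 × 0.55) + 1.282 × √(0.24 + 0.21)]² / 0.30² = 55.7, hence the 56 per arm in 2.3.8.

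**The case against.** A reader might infer that no recording before the scenario exists and that delta HR cannot be derived. The documents do not support that. Section 2.3.6 D says that a baseline will be recorded, no section rules out an earlier reading, and the wait outside the room can supply a pre-entry value. The missing row in Table 1 is weak evidence, since video recording has no row either. What stands is that no reading from before randomisation is described.

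A reader might also infer that control participants will be the more anxious at the door, so that a real benefit of the app is hidden or reversed. The documents give no basis for a direction. Both arms receive the same app training, and the scenario is kept secret until it starts. Control participants work with their usual method, while app participants rely on a tool learned in 5 minutes. Either arm could be the more tense, or neither, and if the arm is still undisclosed at the door there is no route for an effect at all.

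The consequence is limited as well. A participant's own baseline cancels when phases are compared within that participant, and 2.3.14.2 specifies no test or effect estimate between arms. This narrows the point but does not remove it, because 2.3.6 D relates delta HR to preparation method, and reading it that way is a comparison between arms.

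Finally, a reading just before the task has a merit: it separates task stress from anticipation. A seated reading adds anticipation and a change of posture to every delta. That cost applies in both arms and is the lesser one for a comparison by method.

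**Conclusion.** The point holds as a design weakness in a secondary stress marker. Followed as written, the plan yields a baseline taken after randomisation and in anticipation of the task, and delta HR subtracts it in full. The bias in a comparison by method equals the arm difference in that baseline, bpm for bpm, with reversed sign.

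Whether any such difference arises depends on the participant knowing the arm at the door, which the sections leave unresolved. Its size and direction cannot be taken from the documents, so the bpm figures above are illustrations and not estimates. The primary outcome, TDP, TDD and the sample size are unaffected.

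**What to change.** 1. In 2.3.5.1, start the watch after consent and before allocation is opened, and leave it running until the switch-off already planned.
2. In 2.3.6 D, define baseline HR as the mean while the participant completes the demographic questionnaire, and use that value in delta HR. The questionnaire precedes allocation under both orders, so this works whichever is kept.
3. In Table 1, add rows for baseline HR and continuous HR.
4. Reconcile 2.3.5.1, 2.3.7 and 2.3.10.2 (with 2.3.11.1) on when allocation is made and when the participant learns it.
5. Keep HR during the wait outside the room as a separate descriptive segment and not as the baseline. It then shows anticipation by arm.

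Cost: the same watch is fitted some minutes earlier, within the 60-minute slot in 2.3.5.3, with no extra device or visit. The price in interpretation is that delta HR will also include anticipation and posture change, in both arms; this should be stated when the results are reported.

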2.3.5.2. Criteria for discontinuing or modifying interventions

The time needed to complete the full scenario was set to only a 20 minutes period for each participant and will be booked weeks ago to ensure availability of the participants without repercussion on their normal duty. All participants will receive full permission from their hierarchy to participate to the study. Using simulation-based CPR scenario makes our study highly feasible without risks for patients or participants.

2.3.5.3. Adherence

The study will take place during a 1-week period in each EMS and will occupy each paramedic for a single 60-minute period. Thanks to our experience gathered in previous studies, we anticipate a very low rate of drop-outs or loss of follow-up. To ensure the presence of participants on the day of participation, shift-working paramedics will be randomly recruited 1 month before the start of the study by a blinded noninvestigator. They will be informed of the upcoming simulation study but not of its purpose and outcomes. Each paramedic will be rewarded individually by an amount of 50.- CHF for its participation to the study. Adherence of the collaborating EMS to our study will be reinforced by their citation in further publications and by a privileged access to the PedAMINES app.

2.3.5.4. Concomitant care

The paramedics will be allowed to use their current, conventional method of preparing direct IV drugs, even if it differs between EMS. This will avoid introducing evaluation bias on the baseline ability of paramedic to prepare drugs “as usual” if allocated in the group without PedAMINES. This will also test the absolute capacity of the app to reduce medication errors and drugs delays, indifferently of the prior traditional method used.

However, participants will not be allowed to use any other drug support device and the scenario will remain secret until it starts to avoid upstream drugs preparation's refresh.

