2.3.2. Objectives and hypothesis

We aim to determine whether the prehospital use of PedAMINES by EMS in Switzerland reduces medication errors, as well as TDP and TDD.

Research hypothesis: Herein, we hypothesize that PedAMINES reduces medication errors and TDP and TDD independently of existing conventional preparation methods (i.e. precalculated drug dosing charts) or EMS' skills.

Primary objective: To determine whether prehospital use of PedAMINES during pediatric resuscitation reduces medication preparation errors compared with conventional methods.

Secondary objective: To determine whether prehospital use of PedAMINES during pediatric resuscitation reduces dosing deviations and other types of errors (see below) compared with conventional methods. To determine if PedAMINES leads to a shorter time in direct IV drugs preparation (TDP) and delivery (TDD).

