2.3.3. Study design

The study is a prospective, multicenter, randomized controlled trial with 2 parallel groups comparing PedAMINES^{46,47} with conventional precalculated drug dosing charts used by EMS in the preparation of direct IV drugs during a standardized simulation-based pediatric cardiac arrest scenario. The drug dosing charts is presented as a spreadsheet, enabling the preparation of the commonly ordered concentrations of emergency medications at varying dose ranges based on the patient's weight. To calculate the composition of the drug to inject, one first selects the desired drug dosage to be delivered in mg/kg. The next step is to calculate the milliliters of drug based on the weight of the patient to be diluted with compatible fluids (sodium chloride 0.9%, etc) in a syringe. For the purpose of the study, we will not select drugs that can be directly drawn from the vial without calculation and dilution.

The multicentric setting of the study will involve 15 Swiss EMS (Cantons of Geneva, Vaud, Neuchâtel, Fribourg, Jura, Zurich, Bern, Basel, Lucern, Ticino). To ensure optimal quality of reporting, the trial is formatted according to the Consolidated Standards of Reporting Trials Statement for Randomized Controlled Trials of Electronic and Mobile Health Applications and Online TeleHealth (CONSORT-EHEALTH)⁴⁸ and the Reporting Guidelines for Health Care Simulation Research⁴⁹

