2.3.8. Sample size

The primary objective of this study is to detect a difference in proportions of medication errors between groups (with PedAMINES vs without PedAMINES). The expected proportion of errors made without PedAMINES is 60%¹¹. We consider that a difference of 30% in the proportion of medication errors is sufficient to modify the practice. Therefore, the sample size was calculated to reach a statistical power of 90% in detecting an absolute difference of at least 30% in proportions of medication errors between intervention groups. With a two-sided risk alpha of 0.05, the needed sample size is 56 paramedics per arm of the study. To prevent a potential loss of power due to misspecification of assumptions, 60 paramedics will be recruited per randomized group (total sample size: 120 paramedics).

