2.3.14.2. Statistical methods for additional analysis

For the primary and secondary outcomes, logistic regression analyses will be conducted to test a difference in rates of errors between urban EMS (defined as a primary EMS agency in a area populated with 50,000 or more people in the immediate proximity of a tertiary care PED)⁵⁶ and rural EMS (i.e. EMS agency not included within an urban area) with PedAMINES and with the conventional preparation method. In a GEE logistic regression model, an interaction between interventions and urban/rural EMS will be tested to investigate a potential modification of the efficacy of PedAMINES in rural area compared with urban area. Results will also be correlated to the EMS exposition (i.e. total number of emergency calls per year per EMS divided by the number of paramedics working in that EMS). Analyses of primary and secondary outcomes will be conducted in paramedics with more or less than 10 years of experience.

Means and standard deviations will be determined for stress and satisfaction scores (Likert scale) of individuals for each questionnaire item as well as for the UTAUT questionnaire and reported with descriptive statistics. Pearson correlations will be computed between the HR measures obtained with the watch and the scenario phases for each of the drugs and preparation methods used.

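### The pooled comparison can show an average benefit over the conventional methods in use, but not a benefit independent of the method, because no planned analysis involves the method

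*Combined protocol and SAP*

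**What the plan says.** The hypothesis in section 2.3.2 is that "PedAMINES reduces medication errors and TDP and TDD independently of existing conventional preparation methods". The sentence goes on with a parenthesis that equates those methods with dosing charts, and then adds EMS skills. The summary in section 1 makes the same claim. Section 2.3.5.4 allows the method to differ between EMS and presents this as a test: "This will also test the absolute capacity of the app to reduce medication errors and drugs delays, indifferently of the prior traditional method used".

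The comparator is described in two ways. Section 2.3.3 compares the app "with conventional precalculated drug dosing charts used by EMS in the preparation of direct IV drugs", and the outcome definitions in section 2.3.6 measure deviations against the charts or the app. Section 2.3.1 names the length-based tape, protocols or charts.

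In section 2.3.14.1 the models for errors and for TDP/TDD contain arm, type of medication and a random intercept for repeated measures within paramedics. Section 2.3.14.2 adds three analyses: an arm-by-urban/rural interaction, a correlation of results with EMS exposure (calls per paramedic), and this one: "Analyses of primary and secondary outcomes will be conducted in paramedics with more or less than 10 years of experience".

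**The concern.** Allowing methods to vary and then pooling them estimates one average difference against the mix. It does not examine whether the difference is similar for each method. The average part of the hypothesis is tested; the independence part is not.

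The gap matters because sections 1 and 2.5 look ahead to deployment across Switzerland. An EMS that already has a good chart would want to know whether the app improves on that chart. A pooled result could come from a large gain over one method and none over another.

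On skills, two separate analyses by experience give two estimates but no estimate of how far they differ. Readers tend to compare their p-values, which misleads in groups of this size.

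**Working it through.** **Where method and experience enter the plan**

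- Usual conventional method: in no model (2.3.14.1, 2.3.14.2), not among the outcomes (2.3.6), and not among the listed survey topics (2.3.5.1: demographics, care training, simulation and computer experience). Where sections 2.3.6 and 2.3.14.2 speak of preparation methods used, the contrast is app versus conventional, that is, the arm.
- Recall of how the drugs were prepared (2.3.5.1): taken after the scenario as a comprehension check. It cannot show what app-arm paramedics would otherwise have used.
- EMS-level proxies for skill: urban/rural, with an interaction; exposure, as a correlation with no stated link to arm.
- Individual experience: separate analyses only.

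**The plan's own figure**

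Inputs from section 2.3.8: 60% errors without the app; "detecting an absolute difference of at least 30% in proportions of medication errors between intervention groups", hence 30% with the app; power 0.90; two-sided alpha 0.05.

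n per arm = [1.960 × sqrt(2 × 0.45 × 0.55) + 1.282 × sqrt(0.60 × 0.40 + 0.30 × 0.70)]² / 0.30² = (1.379 + 0.860)² / 0.09 = 55.7, rounded up to 56.

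This agrees with "With a two-sided risk alpha of 0.05, the needed sample size is 56 paramedics per arm of the study". At the planned 60 per arm, power is about 0.92. The calculation is correct, and it is for the pooled effect.

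**What the pooled test can distinguish**

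Assume two equally common methods with 60% control errors under each:

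- effects of 30 and 30 points: app errors 30% and 30%, average 30%
- effects of 45 and 15 points: app errors 15% and 45%, average 30%
- effects of 60 and 0 points: app errors 0% and 60%, average 30%

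The pooled comparison is 60% versus 30% each time, with power about 0.92 each time. A significant result does not separate these cases.

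**What a contrast between methods could show**

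The documents give no split of methods, so an even split (30 per arm for each method) with 60% versus 30% in both is assumed.

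- SE of the arm difference within one method: sqrt((0.24 + 0.21) / 30) = 0.122
- SE of the difference between two such effects: 0.122 × sqrt(2) = 0.173
- 95% half-width for one drug: 1.96 × 0.173 = 0.339
- Over four drugs, multiply by sqrt((1 + 3 × ICC) / 4): 0.194 at ICC 0.1, 0.234 at 0.3, 0.268 at 0.5
- With a 25:75 split and one drug: SE = sqrt(0.45/15 + 0.45/45) = 0.200, half-width 0.392

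For one drug, the difference between effects detectable with 80% power is 2.80 × 0.173 = 0.49 (even split) or 2.80 × 0.200 = 0.56 (25:75). Power to detect 45 versus 15 points is about 43% and 36% respectively. The extreme case of 60 versus 0 would be detected with about 97% power under the even split, but only if method were recorded and analysed.

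**Separate analyses by experience**

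Assume again 30 per arm in each half, one binary outcome per paramedic, and the same true effect (60% versus 30%) in both. Power within each half is 0.653. The chance that exactly one half is significant is 2 × 0.653 × (1 − 0.653) = 0.45. Identical effects would therefore look different in nearly half of such trials.

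**The case against.** The strongest reply is that this is a pragmatic comparison with usual care. The primary objective in section 2.3.2 refers simply to conventional methods, and sections 2.3.8 and 2.3.14.1 size and analyse that average contrast. Section 2.3.5.4 may mean no more than the app against whatever each EMS uses. That stands for the primary test, the sample size and the randomised comparison, none of which is in question. A reader might infer that the pooled result cannot support the hypothesis at all. The documents do not support that: it supports the average reduction, and only the independence clause lacks an analysis.

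A reader might also infer that skills are ignored. They are not. The urban/rural interaction and the exposure correlation bear on EMS-level skill, although the correlation is loosely specified and neither uses individual experience.

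Nor is all information on method lost. Video (2.3.12.1) and the recall interview could give the method used by the control arm, and EMS is a randomisation stratum (2.3.10.1). The app arm's usual method would still have to be recorded.

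The parenthesis in section 2.3.2 could be read as making charts the only comparator. Sections 2.3.1 and 2.3.5.4 say otherwise, so this adds to the inconsistency.

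Objections to an analysis by method also stand, and they limit what it can conclude:

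- Method is not randomised and is confounded with other features of the 15 EMS.
- Use of equipment is left to the individual (2.3.5.1), so one label per EMS may misclassify people.
- Tape and charts may be used together, as in an intervention described in section 2.1.
- The father states the child's weight in the scenario, so weight estimation by tape is not exercised.
- App error rates of 0% and 10.2% in the earlier in-hospital trials (2.2) suggest sparse cells.

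**Conclusion.** The concern holds for the independence clause only. The plan can support an average reduction in errors, TDP and TDD against the conventional methods in use. It cannot support the statement that the benefit holds regardless of method, because the pooled contrast is the same for effects of 30/30 and 60/0 and nothing in the plan looks further. Skills are partly addressed at EMS level, but the planned experience analyses do not test whether effects differ.

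Even with the data recorded, a contrast between methods would be imprecise: about ±34 points for one drug, or ±19 to ±27 over four. These figures rest on two equal groups, 60% versus 30% errors in each, ICC 0.1 to 0.5 and no between-EMS variation in effect. Three methods, unequal groups or varying effects would widen them. Consistency across methods can therefore be described but not concluded. The change is worth making before the trial starts, since usual method in the app arm is hard to reconstruct afterwards.

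**What to change.** 1. In section 2.3.14.2, replace the separate experience subgroups with an arm-by-years-of-experience interaction (years continuous) in the primary and TDP/TDD models, reported with its 95% CI. This also removes the question of where exactly 10 years belongs.
2. Record usual method or methods before allocation, at the preparatory EMS visit already scheduled in section 2.4 and as one item on the baseline survey, allowing more than one answer. Report the arm difference with 95% CI by usual method, plus an arm-by-method term, all labelled exploratory. State that method is not randomised, that it is confounded with other EMS features, and that intervals will be wide.
3. Reword the claims in sections 1, 2.3.2 and 2.3.5.4 to an average effect compared with the mix of conventional methods in use, with consistency across methods described rather than concluded.
4. Reconcile the comparator: charts only in sections 2.3.2 (parenthesis), 2.3.3 and 2.3.6, against tape, protocols or charts in 2.3.1 and methods that may differ by EMS in 2.3.5.4.

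Cost: one or two data fields, two model terms and wording. The price is imprecise exploratory estimates and a more modest claim. Sample size, randomisation and the primary test do not change.
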